10.1. Overall

Name of data	Derivation and calculation methods
Age	The age on the start date of treatment should be calculated. However, if the birth date is unknown, the age described in the CRF should be used. Since it is obtained up to birth month and year in the CRF, the birth date should be the 1st of the month.
Number of survey institutions	It should be tabulated by institution code.
Number of patients surveyed	It should be tabulated by case (number).
Calculation of period	Period = the relevant date - the initial date +1
Definition of unit period	One week should be converted into seven days.
Date of initial Humira treatment	Of the start dates of treatment in Humira treatment status, the earliest date should be the date of initial Humira treatment.
Date of final Humira treatment	
Of the completion dates of treatment in Humira treatment status, the latest date should be the date of final Humira treatment.
 
However, the following measures should be taken according to the final record of each patient.
 
 • For patients whose the start date of treatment exceeds the planned completion date of each CRF and the completion date of treatment is described as “continuing,” the start date of treatment should be complemented to the complete date of treatment of the record. • For patients whose the start date of treatment is prior to the planned completion date of each CRF and the completion date of treatment is described as “continuing,” the completion date of treatment should be complemented to the complete date of treatment of each CRF. • If the start date of treatment with a biological product and the final record of the completion date of Humira treatment are the same date in the third CRF, the completion date of Humira treatment should be -1 day and the overlap of the treatment period should be deleted. 
*Planned completion date of each CRF First CRF: start date of Humira treatment + 167 days Second CRF: start date of Humira treatment + 363 days Third CRF: start date of Humira treatment + 727 days

Period to treatment completion (day)	It should be between the date of initial Humira treatment and the date of final Humira treatment.

Name of data	Derivation and calculation methods

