Treatment period (day) Completion date of treatment *Per record	
It should be between the start date of Humira treatment and the completion date of treatment per treatment record.
 
When the completion date of treatment in the information on the previous treatment within the same CRF and the start date of treatment in the information on the relevant treatment are the same date, the completion date of treatment in the information on the previous treatment should be - 1 day.
 
The records with the dose of 0 mg should be excluded from the analysis.

Dosing intervals (day) *Per record	Biweekly should be 14 days, once in three weeks should be 21 days, and once in four weeks should be 28 days, respectively.
Total number of doses	The total after calculating the number of doses per record by rounding up the first decimal place should be taken for treatment period (day)/dosing intervals (day).
Patients who discontinued Humira treatment	If the final fixed CRF is the first or second CRF, the patients should be handled as the patients with a description in the “treatment discontinuation” column in the final CRF. If the final fixed CRF is the third CRF, the patient should be handled as the patients with a description of the completion date of treatment in the final record of the “Humira treatment status” column in the final CRF.
Patients who are continuing Humira treatment	If the final fixed CRF is the first or second CRF, the patients should be handled as the patients without a description in the “treatment discontinuation” column in the final CRF. If the final fixed CRF is the third CRF, the patient should be handled as the patients with a description of “continuing” in the final record of the “Humira treatment status” column in the final CRF.
Date of treatment discontinuation	In patients who discontinued Humira treatment, the completion date of Humira treatment should be the date of discontinuation.
Low body weight	Patients with body weight of < 30 kg.
Date of survey discontinuation	It should be the date of survey discontinuation described in the third CRF. It should be the start date of treatment with other biological products, or the older date among the last follow-up date.
AE follow-up period	It should be between the date of initial Humira treatment and the date of initial Humira treatment + 755 days.

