10.2. Safety analysis

Name of data	Derivation and calculation methods
Adverse event	For adverse event-related data, “an AE matching list”, the data set through the matching activities (matching of CRF data and safety information data), should be used. AEs with the same patient number should be aggravated and counted as one event when the PT is the same. However, when the novelty (known/unknown) is different within the same PT, such as in Appended Form 2, they should be tabulated separately.
Seriousness of AE	For seriousness of an AE aggravated from a single patient as the same PT, seriousness set through AE matching activities should be set in the following order of priority. Serious Non-serious
Causal relationship of AE	Where the causal relationship set through AE matching is other than “not related”, the causal relationship is defined as related. For causal relationship of an AE aggravated from a single patient as the same PT, causal relationship set through AE matching activities should be set in the following order of priority. Related Not related
Outcome of AE	Outcomes of AEs aggravated from a single patient as the same PT should be set in the following order of priority. Fatal Unknown Not recovered/Not resolved Recovered/Resolved with sequelae Recovering/Resolving Recovered/Resolved
Adverse reaction	AEs of which causal relationship is other than “not related” set through the AE matching activities are defined as ADRs.
Serious AEs	AEs of which seriousness set through the AE matching activities is “serious” are defined as serious AEs.
AEs outside the follow-up period	These should be handled as outside the safety analysis. AEs are defined that occurred prior to the start date of Humira treatment or at week 108 (treatment start date + 755).

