“5.2.3 Summary of serious adverse drug reactions by each MTX Dose of Baseline”

Analysis object: Patients included in the safety analysis set

Purpose of analysis: To indicate the number of patients analyzed, number of patients who developed ADRs, number and percentage of ADRs, number and percentage of SOC and PT by category of MTX dose at the start of treatment regarding serious ADRs.

Note: Category of MTX dose at the start of treatment

“Baseline MTX 12<= $<$ 14.0,” “Baseline MTX 14.0<= $<$ 16.0,” “Baseline MTX 16.0<=”

This should be prepared only at the time of literature analysis.

“Table 5.2.4 Summary of serious adverse drug reactions by each MTX Dose of Baseline (Event/100 Patient Years)”

Analysis object: Patients included in the safety analysis set

Purpose of analysis: To indicate the number of patients analyzed, number of patients who developed ADRs, number and percentage of ADRs (unit: 100 persons/year), number and percentage of SOC and PT by category of MTX dose at the start of treatment regarding serious ADRs during Humira treatment.

Note: Category of MTX dose at the start of treatment

“Baseline MTX 12<= $<$ 14.0,” “Baseline MTX 14.0<= $<$ 16.0,” “Baseline MTX 16.0<=”

Percentage of patients who develop ADRs (person/year) = “number of serious ADRs / total follow-up period)

This should be prepared only at the time of literature analysis.

“Table 5.3.1 List of AEs occurred during treatment and after completion of treatment”

Analysis object: Patients included in the safety analysis set

Purpose of analysis: To indicate the number of overall ADRs, SOC and PT occurred by case status (overall, patients who are continuing Humira treatment, patients who discontinued Humira treatment) regarding AEs.

The patients who discontinued Humira treatment should be indicated by timing of treatment (during treatment, after treatment).

Note: The definitions of case status should be as follows.

- During treatment

Events that occurred between the date of initial Humira treatment and the date of final Humira treatment.

- After treatment

Events that occurred after the date of final Humira treatment.

“Table 5.3.2 List of serious AEs occurred during treatment and after completion of treatment”

Analysis object: Patients included in the safety analysis set

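### SAP Table 5.2.4 counts serious ADRs on treatment but divides by an undefined total follow-up period, so its rate per 100 patient-years mixes two different spans of time

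*SAP*

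**What the plan says.** SAP 13.2, Table 5.2.4, is headed as a rate ("Event/100 Patient Years") in three baseline MTX dose groups. Its purpose line restricts the table to on-treatment events: "regarding serious ADRs during Humira treatment". Its note gives the formula as "number of serious ADRs / total follow-up period". The same note calls the result a percentage of patients, although the numerator is a count of reactions, and the formula shows no factor of 100. Table 5.3.1 in the same section takes on-treatment to mean from the first to the final Humira date.

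No entry in the SAP defines a total follow-up period. Two nearby terms in SAP 10.1 are defined:

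- The AE follow-up period: "It should be between the date of initial Humira treatment and the date of initial Humira treatment + 755 days". It is not cut at treatment or survey discontinuation.
- The period to treatment completion: "It should be between the date of initial Humira treatment and the date of final Humira treatment". Table 5.2.4 does not refer to it.

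SAP 10.2 sets the general counting rule, under which events in one patient are "counted as one event when the PT is the same".

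Protocol 7.5 ends a patient's observation when adalimumab stops, if that happens within 52 weeks. After week 52, observation ends only when another biologic is given.

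**The concern.** A person-time rate needs the same time at risk above and below the line. Here an event counts only while the patient is on Humira, but the named denominator can include time when no event could count. Such time can only lower the rate.

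Two analysts could follow this text and report clearly different numbers. One who looks up follow-up period in SAP 10.1 finds a fixed window that is the same for every patient. For early discontinuers, that window adds months after the protocol has ended observation. Another analyst might sum each patient's actual follow-up. That still includes off-drug time for patients who stop after week 52 and stay in the survey.

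Table 5.2.4 is the SAP's only person-time safety rate. Table 5.2.3 already gives crude figures for the same MTX groups, so Table 5.2.4 exists to account for exposure, and a mismatched denominator defeats that. The table is meant for the literature analysis, where readers may set its rates beside those of other studies.

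**Working it through.** **Length of the fixed window.** SAP 10.1 gives the counting rule "Period = the relevant date - the initial date +1". With an end at day +755, the length is 755 + 1 = 756 days = 108 × 7. This agrees with the week 108 limit in SAP 10.2.

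**Inputs.** Protocol 13.1 gives 32% dropout by week 24 (from the all-case survey) and assumes 50% by week 52. I take these as retention on drug: 0.68 at day 168 and 0.50 at day 364. The documents give no loss between weeks 52 and 104. I assume that 0-30% of those remaining stop, with 50% as a stress case.

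**Mean time on drug per patient.** Within each interval, retention is assumed to fall exponentially from a to b over d days. Time on drug is then (a − b) × d / ln(a/b), or a × d if a = b.

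- Days 0-168: (1 − 0.68) × 168 / ln(1/0.68) = 53.76 / 0.3857 = 139.4
- Days 168-364: (0.68 − 0.50) × 196 / ln(0.68/0.50) = 35.28 / 0.3075 = 114.7
- Days 364-728, no further loss: 0.50 × 364 = 182.0
- Days 364-728, 30% loss: (0.50 − 0.35) × 364 / ln(0.50/0.35) = 54.6 / 0.3567 = 153.1
- Days 364-728, 50% loss: (0.50 − 0.25) × 364 / ln 2 = 91 / 0.6931 = 131.3

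**Observed follow-up per patient.** Observation ends at drug stop before week 52. Otherwise it is taken to day 728 with no switch to another biologic, which allows the most off-drug time: 139.4 + 114.7 + 182.0 = 436.1 days.

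| Later loss (assumed) | Mean days on drug | Shortfall with 756 days | Shortfall with observed follow-up (436.1 days) |
|---|---|---|---|
| 0% | 436.1 | 1 − 436.1/756 = 42% | 0% |
| 30% | 407.2 | 1 − 407.2/756 = 46% | 1 − 407.2/436.1 = 7% |
| 50% | 385.4 | 1 − 385.4/756 = 49% | 1 − 385.4/436.1 = 12% |

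Linear instead of exponential decline gives nearly the same result: 438.8 days with no later loss (42%) and 393.3 days with 50% (48%).

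**Lower dropout, 756-day reading.** With assumed retention of 90/80/70% at weeks 24/52/104 and linear decline, mean time on drug is 599.2 days and the shortfall is 1 − 599.2/756 = 21%. With no dropout at all it is 1 − 728/756 = 4%.

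**Between MTX groups.** With equal retention, every group's rate is scaled alike and the ratio stays 1.0 on either reading. As an illustration only, let one group lose 20% by week 24 and 30% by week 52, let another lose 32% and 50%, and let 15% of those remaining stop later in both. Mean time on drug is 532.5 and 422.1 days; observed follow-up is 552.2 and 436.1 days. For equal true rates:

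- 756-day reading: apparent ratio 532.5/422.1 = 1.26
- Observed-follow-up reading: (532.5/552.2) / (422.1/436.1) = 0.964/0.968, about 1.0

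**The case against.** The strongest reply is that the 756 days belong to a different term. SAP 10.1 defines them for the AE follow-up period, which the SAP uses to decide which events are admitted, never as person-time. The SAP also refers elsewhere to each patient's last or final follow-up date. In a table of patient-years, summed actual follow-up is at least as natural a reading. This stands: a reader might infer that the plan prescribes 756 days and that rates will be almost halved, but the text does not say so. On the alternative reading the shortfall is small, because the protocol ends observation at drug stop before week 52 and the planned 50% dropout then adds no off-drug time.

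A reader might also infer that the MTX comparison is biased. The documents give no retention by dose, so the 1.26 above shows only what could happen, and only on the 756-day reading.

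Importance is limited too. The study is single-arm, its primary objective is DAS28 below 2.6 at week 52, and Table 5.2.4 specifies no test. Counting repeats of the same preferred term (PT) once per patient is the SAP's general rule and not an error of this table. Dropping it here would separate the table from its companion, Table 5.2.3.

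What survives is the mismatch. The named denominator is undefined, neither follow-up reading is confined to treatment, and the matching quantity is already in SAP 10.1 but is not used.

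**Conclusion.** The point holds as a mismatch between an on-treatment numerator and an undefined denominator that is not limited to treatment. At the plan's own dropout, with an assumed 0-30% later loss, the rate is about 42-46% too low if 756 days per patient is used. It is about 0-7% too low if observed follow-up is used, rising to about 12% with 50% later loss. These figures assume that survey dropout equals stopping adalimumab, that exposure is cut at day 728, and, for the second reading, that nobody switches biologic after week 52. The documents do not settle which reading applies, so neither range is a prediction. Distortion between MTX groups is possible but not shown. The table serves the literature analysis only; the primary endpoint and sample size are unaffected. It should be corrected before that analysis is run.

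**What to change.** In SAP Table 5.2.4:

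- Define the denominator as the sum over patients of (date of final Humira treatment − date of initial Humira treatment + 1) / 365.25.
- Cut each patient's time at the initial date + 755 days, the limit that already applies to the numerator. The period to treatment completion has no cap of its own, so without this cut, time in which no event can count would enter the denominator.
- Multiply by 100, and call the result an event rate instead of a percentage of patients.
- State that repeats of the same PT in one patient are counted once, as in SAP 10.2.

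The note to Table 3.1 says that the period to treatment completion includes washout. Gaps between the first and final dates therefore stay in the denominator, which agrees with the first-to-final definition of on-treatment events in Table 5.3.1.

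The cost is SAP wording only, since the dates are already derived. Reported rates will be higher than, or at least equal to, those under either follow-up reading.

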7.5 Study Duration

- 1) The duration of the whole PMOS is estimated to be about 4 years.

- Study start: September 2012
-

- Recruiting phase: September 2012 - December 2014
 - Data completion: January 2018
 - End of study: The date on which statistical analysis dataset for Clinical Study Report becomes available
 - Data analysis and final report: April 2018 – October 2018
- 2) For each individual patient, the PMOS starts with the enrollment at the beginning of the treatment with adalimumab.
- Observation period
 - 104 weeks (or discontinuation of this study)
 - Discontinuation of this study
 - Patients within 52 weeks into this study: When adalimumab treatment is discontinued.
 - Patients after 52 weeks into this study: When any biologics other than adalimumab is administered.

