12.0 Case Report Forms

All data specified in Section 8.5 "Study Conduct" will be collected on paper forms (CRF). For each visit, the CRF includes forms to be completed by the physician as well as forms to be completed by the patient. Each center receives a folder with all documents and forms necessary for the baseline and follow-up documentation of contract number of cases.

Any observation of an adverse event in the time period up to 104 weeks (or discontinuation of this study), beginning with the initiation of adalimumab therapy, is to be documented on the CRF. If the event fulfills the serious criterion (Serious Adverse Event), the "Serious Adverse Event Report" form is to be completed additionally.

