13.1 Sample Size Calculation

The primary endpoint of this study is the proportion of subjects who achieve DAS28 (CRP) remission (DAS28 <2.6) after 52 weeks of adalimumab + high dose MTX. We calculated the target sample number for this survey on the basis of an expected remission

rate, i.e., the percentage of patients with a DAS28 score of <2.6, at week 52 during the treatment with adalimumab 40 mg and MTX at ≥ 12 mg/week.

Table 3 lists the percentages of patients with a DAS28 score of <2.6 at week 52 in a study conducted by Takeuchi et al.⁹⁾ in patients receiving adalimumab and MTX.

Table 3. Patients with a DAS 28 score of <2.6 at week 52 during the treatment with adalimumab and MTX

adalimumab + MTX dose (mg/week)	Percentage of patients with DAS28 <2.6 (Week 52)
8.5 ± 2.9	42.7% (61/143 patients)
≥ 12	61.7% (29/47 patients)

As Table 3 shows, 42.7% of patients receiving MTX at 8.5 ± 2.9 mg/week at the initiation of adalimumab treatment achieved a DAS 28 of <2.6 at week 52, and the corresponding percentage of patients receiving DAS at ≥ 12 mg/week at baseline was 61.7%. When 55% of patients receiving MTX at ≥ 12 mg/week at the initiation of adalimumab treatment are assumed to achieve a DAS 28 of <2.6 at week 52 (subtracting the standard error (7.10%) from the above mentioned percentage; $61.7 - 7.1 = 54.6\%$), the number of patients required to achieve a power ($1-\beta$) of 0.90 at an α level of 0.05 (two-tailed) would be 171 (one-sample test).

Since 32% of patients enrolled in the all-case survey of adalimumab in patients with rheumatoid arthritis dropped out during the 24-week survey period, we assumed that 50% of the participants in the survey would drop out during the 52-week survey period, and calculated that 342 patients should enroll in the survey. We thus set the target sample size at 350.

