4.3. Planned sample size

(1) Planned number of patients surveyed

350 patients

(2) Rationale for setting

The patient with Disease Activity Score 28 (hereafter, referred to as “DAS28”) below 2.6 at week 52 was estimated to be 55% (the expected observation was 55% and the estimated difference was 12.3% for the literature data 42.7%), and the number of patients required to detect at a 5% level of significance level (paired) and a 90% power was calculated to be 171 patients. As the number needed to treat to secure this number of patients, the dropout rate at week 52 in this survey was assumed to be 50% based on the dropout rate of approximately 32% at week 24 in the all-case surveillance with Humira, and the planned number of patients surveyed was calculated to be 350 patients.

5. Items to be evaluated in analysis and examining method

(1) Analysis items

1) Matters concerning patient composition

- 1) Number of patients with returned CRFs
- 2) Number of patients included in the safety analysis set
- 3) Number of patients included in the efficacy analysis set

- 2) Matters concerning safety
 - 1) List of incidences of ADRs/infections
 - 2) Factors considered to have an influence on safety
Incidence of ADRs by patient background factor, etc.
 - 3) AEs occurred during or after treatment
List of incidences of serious AEs, etc.
 - 3) Matters concerning efficacy
 - 1) DAS28 response, trend, percentage of remission, etc.
 - 2) CDAI response, trend, percentage of remission, etc.
 - 3) SDAI response, trend, percentage of remission, etc.
 - 4) Trends in HAQ, etc.
 - 5) Trends in EQ-5D, etc.
 - 6) Trends in mTSS/bone erosion score/joint space narrowing score and the percentage of patients without worsening of mTSS/bone erosion score/joint space narrowing score (change from the survey start < 0 and < 0.5), etc.
 - 7) Factors considered to have an influence on efficacy (list of efficacy by patient background factor, etc.)
- (2) Analysis methods
Appropriate methods including χ^2 test according to the scale and nature of the analysis data should be used.

6. Schedule of the analysis

Purpose of the analysis	Survey unit period and time frame for reexamination
The 11th Periodic Safety Report	December 31, 2012 - June 30, 2013
The 12th Periodic Safety Report	July 1, 2013 - December 31, 2013
The 13th Periodic Safety Report	January 1, 2014 - June 30, 2014
The 14th Periodic Safety Report	July 1, 2014 - December 31, 2014

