Purpose of analysis: To indicate the number of overall patients with fixed CRFs and by CRF for the patients included in the safety analysis set and efficacy analysis set.

Note: None in particular.

“Table 1.3.2 List of patients”

Analysis object: Patients with fixed CRFs

Purpose of analysis: To confirm the details of the overall patients.

Note: To indicate the details in a list.

“Table 1.3.3 Lists of patients excluded from safety analysis set and patients excluded from efficacy analysis set (including reasons for exclusion)”

Analysis object: Patients excluded from the safety analysis set, patients excluded from the efficacy analysis set

Purpose of analysis: To confirm the reasons for excluding from the safety analysis set and efficacy analysis set.

Note: To indicate the case numbers and reasons for exclusion in a list.

<Detailed note>

*Where one patient has more than one reason for exclusion, they should be linked with “commas” for output.

“Table 1.4 Disposition by Hospital of the University of Occupational and Environmental Health, Japan”

Analysis object: Patients included in the safety analysis set, patients included in the efficacy analysis set (DAS28-4CRP)

Purpose of analysis: To indicate the incidence of ADRs and the results of χ^2 tests in the patients included in the safety analysis set and the response rate in EULAR DAS28-4CRP and the results of χ^2 tests in EULAR DAS28-4CRP at the final evaluation in patients included in the efficacy analysis set (DAS28-4CRP) per institution analyzed (other than Hospital of the University of Occupational and Environmental Health, Japan and University of

Occupational and Environmental Health, Japan).

Note: Good Response and Moderate Response should be judged as “effective” for the EULAR DAS28-4CRP response at the final evaluation.

“Table 1.5 Disposition by mode of Humira administration”

Analysis object: Patients included in the safety analysis set, patients included in the efficacy analysis set (DAS28-4CRP)

Purpose of analysis: To indicate the incidence of ADRs and the results of χ^2 tests in the patients included in the safety analysis set and the response rate in EULAR DAS28-4CRP and the results of χ^2 tests at the final evaluation in patients included in the efficacy analysis set (DAS28-4CRP).

The category for mode of administration should follow “11. Data-layer separation.”

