Purpose of analysis: To indicate the number of overall AEs, SOC and PT occurred by case status (overall, patients who are continuing Humira treatment, patients who discontinued Humira treatment) per timing of treatment (during treatment, after completion of treatment) regarding serious AEs.

Note: The definitions of the patients who are continuing Humira treatment and the patients who discontinued Humira treatment should be same as “Table 5.3.1 List of AEs occurred during treatment and after completion of treatment.”

“Table 5.4 Incidence of ADRs by patient background factor”

Analysis object: Patients included in the safety analysis set

Purpose of analysis: To indicate the overall ADRs, and the number and percentage the patients who developed ADRs by seriousness by patient background factor. The categories of patient background factors should follow “11. Data-layer separation,” and when ADRs of the same PT occurred in the same patient, and the number of the ADR should be rounded to a severe event before tabulation.

<Detailed note>

- 1) The data at the start of Humira treatment should be analyzed.

- 2) The data during the Humira treatment should be analyzed.

“Table 5.4.1 Incidence of ADRs by patient background factor (Hospital for the University of Occupational and Environmental Health, Japan)”

Analysis object: patients included in the safety analysis set

Note: Patients treated at the Hospital of the University of Occupational and Environmental Health, Japan should be tabulated.

“Table 5.4.2 Incidence of ADRs by patient background factor (other than Hospital for the University of Occupational and Environmental Health, Japan)”

Analysis object: patients included in the safety analysis set

Note: Patients excluded from those treated at the Hospital of the University of Occupational and Environmental Health, Japan should be tabulated.

“Table 5.5.1.1 Frequency of ADRs by seriousness with or without liver disorder”

Analysis object: Patients included in the safety analysis set

Purpose of analysis: To indicate the number of patients analyzed, number of patients who developed ADRs, number and percentage of ADRs, number and percentage of SOC and PT by seriousness with or without liver disorder regarding ADRs. Additionally, the stratified items with a significant difference in Table 5.4 should also be tabulated.

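### Table 5.4 compares crude ADR percentages between background groups without allowing for unequal observation time, which can create or mask differences

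*SAP*

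**What the plan says.** - **Measure.** SAP 13.2, Table 5.4: "To indicate the overall ADRs, and the number and percentage the patients who developed ADRs by seriousness by patient background factor". The denominator is patients in the safety set. The entry gives no person-time and names no test.
- **Purpose and use.** SAP section 5 lists ADR incidence by background factor under "Factors considered to have an influence on safety" and names the χ² test as one appropriate method. Table 5.5.1.1 then uses the result: "Additionally, the stratified items with a significant difference in Table 5.4 should also be tabulated".
- **Same comparison by site.** SAP 13.1, Table 1.4, sets the lead hospital against other sites: "To indicate the incidence of ADRs and the results of" χ² tests.
- **End of observation.** Protocol 7.5 defines discontinuation of the study: "Patients within 52 weeks into this study: When adalimumab treatment is discontinued". After week 52 observation ends only when another biologic is given. Protocol 12.0 sets what goes on the CRF: "Any observation of an adverse event in the time period up to 104 weeks (or discontinuation of this study". Protocol 9.3 sets the same end for SAEs.
- **Expected loss.** Protocol 13.1: "we assumed that 50% of the participants in the survey would drop out during the 52-week survey period". This is extrapolated from 32% at 24 weeks in the all-case survey.
- **A different AE window.** SAP 10.1 runs the AE follow-up period from first Humira treatment to day +755 for every patient, and SAP section 12 retains AEs after the end of treatment within that window.
- **Existing exposure-based table.** Table 5.2.4 gives events per 100 patient-years, but only for serious ADRs, only by baseline MTX dose and only in the literature analysis. Its denominator is a total follow-up period that is not defined further.

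**The concern.** Every patient counts as one unit, whether observed for a few weeks or for two years. A group that stops adalimumab sooner because of inadequate response, refusal or missed visits has less time in which a first ADR can be recorded. Its percentage is then lower at the same underlying hazard, so the comparison mixes ADR risk with treatment persistence.

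Both kinds of error are possible. A harmless factor can be flagged because its levels differ in persistence, and a factor with a real excess can look neutral. SAP 3.1 says the results feed reports to the authorities and the reexamination application, so a wrong reading of a risk factor has consequences even in a descriptive survey.

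**Working it through.** **1. The plan's own figure.** Protocol 13.1 and SAP 4.3: p0 = 0.427, p1 = 0.55, two-sided α = 0.05, power 0.90.

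n = [1.960·√(0.427·0.573) + 1.282·√(0.55·0.45)]² / 0.123² = 170.7, rounded up to 171. With 50% dropout, 171/0.5 = 342, set to 350. Both reproduce. The documents give no ADR rate, no dropout by factor and no power for Table 5.4, so those inputs below are assumptions.

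**2. Model.** Dropout d by week 52 gives a stopping hazard g = −ln(1−d) per year in year 1 and none afterwards. Stopping is independent of ADRs, and the ADR hazard is λ per year. The crude two-year percentage is

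P = λ/(λ+g)·[1−e^−(λ+g)] + e^−(λ+g)·[1−e^−λ].

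**3. Same hazard in both groups, λ = 0.2.**
- d = 40%: g = 0.511, P = 0.281·0.509 + 0.491·0.181 = 23.2%.
- d = 60%: g = 0.916, P = 0.179·0.673 + 0.327·0.181 = 18.0%.
- Ratio 18.0/23.2 = 0.77. For λ from 0.1 to 0.5 the ratio is 0.77 to 0.79. At 30% versus 70% it is 0.58 to 0.62.

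**4. Another dropout shape.** Retention of 0.68 at week 24, 0.50 at week 52 and 0.40 at week 104 (the last is assumed), with stopping hazards multiplied by ln(1−d)/ln(0.5). With full follow-up the 104-week ADR risk is 40%.

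| Week-52 dropout | Crude ADR % | Ratio | χ² rejection, 175 per group |
|---|---|---|---|
| 45% vs 55% | 25.5 vs 22.2 | 0.87 | 11% |
| 40% vs 60% | 27.1 vs 20.5 | 0.76 | 31% |
| 35% vs 65% | 28.7 vs 18.8 | 0.65 | 59% |

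Check of the middle row: pooled 23.8%, SE = √(2·0.238·0.762/175) = 0.0455, z = 0.0661/0.0455 = 1.45, Φ(1.45−1.96) = 0.31. The nominal rate is 5%.

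**5. Front-loaded ADRs.** With a hazard five times higher in the first 24 weeks (assumed), the 40/60 ratio is 0.86 to 0.87 under the step 2 dropout model (λ = 0.1 and 0.2) and about 0.84 under the step 4 shape. The distortion is smaller because more first ADRs fall before most of the stopping.

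**6. Masking.** In the step 2 model at 40/60, a true rate ratio of 1.33 to 1.46 in the shorter-observed group gives equal percentages. With λ = 0.2, a true rate ratio of 2 and 175 per group, power is 0.87 if dropout is 50% in both groups and 0.38 at 40/60.

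**7. Where the bias is absent or limited.**
- Dropout of 50% in both groups: 20.7% in each at λ = 0.2, ratio 1.00.
- ADRs themselves cause the stopping, with the same non-ADR stopping hazard of 0.4 per year and a true rate ratio of 2: 25.0% vs 42.4% at λ = 0.2 (ratio 1.69) and 34.5% vs 54.5% at λ = 0.3 (ratio 1.58). The first ADR is counted before the patient stops, so the excess stays visible but smaller than 2.

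**8. Does a simple rate cure it?** With a constant hazard, yes: the rate ratio is 1.00. With the fivefold early hazard, λ = 0.2 and 40/60, first ADRs per patient-year at risk are 0.438/0.863 = 0.508 and 0.381/0.679 = 0.561. That is a spurious ratio of 1.10 against the early stoppers. The comparison must therefore allow the hazard to change over time.

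**The case against.** The strongest points on the other side are these.

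- **The bias is conditional.** It needs persistence that differs by factor for reasons other than ADRs. The 50% is an overall planning figure for the efficacy sample size, and the 32% belongs to the earlier all-case survey. AEs are themselves a listed reason for discontinuation in SAP section 11. This stands: the sizes above are illustrations.
- **Follow-on tables.** A reader might infer that a masked factor suppresses the follow-on tables for elderly patients, liver or renal disorder, or the lead hospital. It does not. Tables 5.5.1.1 to 5.5.1.3 are prespecified subject only to a patient-count rule, and Tables 5.1.3, 5.1.4, 5.4.1 and 5.4.2 cover the lead hospital without any such rule. Only the additional items chosen by significance in Table 5.4 are affected.
- **AE window.** The SAP's day +755 period and post-treatment category could mean that events after an early stop are captured. An analysis window cannot supply events that the protocol does not collect, and post-treatment AEs can come from patients who stop after week 52. How far events after a year-1 stop are recorded is unclear, so this qualifies the point without removing it.
- **Exploratory status and open methods.** The survey is single-arm and largely descriptive, and SAP section 5 allows methods other than χ². That lowers the stakes. No time-based method is specified for this table, however, and its significance result is used.
- **Time-based methods have their own traps.** A constant-rate Poisson model misleads when ADRs are front-loaded. A time-to-event test from day 0 on factors defined during treatment would add immortal-time bias. Both stand and shape the fix.

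**Conclusion.** The point holds in conditional form. Table 5.4 and the ADR part of Table 1.4 compare crude percentages although, under the protocol, observation time can differ widely between patients. If dropout by week 52 were 40% in one group and 60% in another for non-ADR reasons, an equal hazard would show as a crude risk ratio of about 0.76 to 0.79 with a constant hazard, or about 0.84 to 0.87 with a fivefold early hazard. A true rate ratio of 1.33 to 1.46 could be cancelled under the constant-hazard model. These sizes rest on assumed dropout splits, ADR rates and independent stopping.

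A reader might infer that factors which shorten treatment will necessarily look safer and that real harms will be hidden. The documents do not support that. Equal dropout gives no bias, and an excess that itself causes stopping remains visible though reduced. The accurate statement is that the table can mislead in either direction and that the plan gives no means of telling. This is a worthwhile, inexpensive improvement to an exploratory safety analysis and does not touch the primary endpoint.

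**What to change.** 1. Keep the crude percentages in Tables 5.4 and 1.4.
2. For factors fixed at the start of Humira treatment, and for site in Table 1.4, add total observation time and first ADR per 100 patient-years per level.
3. Base the comparison, and the choice of additional 5.5.1 items, on a log-rank test of time to first ADR or on a Poisson model with separate rates for weeks 0 to 24, 24 to 52 and 52 onward. Censor at the end of AE observation.
4. Do not apply a day-0 time-to-event test to factors defined during treatment (concomitant drugs during treatment, mode of administration). Report them descriptively or model them as time-dependent.
5. Reconcile the SAP's day 0 to +755 period and post-treatment AE rule with the protocol's end of observation in year 1, and state one definition of observation time. Define the total follow-up period in Table 5.2.4 in the same way.

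**Cost.** SAP wording and one or two extra columns. SAP 10.1 already derives treatment-stop and survey-discontinuation dates. It does not derive an ADR onset date, but SAP section 12 already tabulates by first occurrence. Some factors flagged by χ² may change. The test assumes that censoring is unrelated to ADR risk, which is why observation time per level should be shown beside it.
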